## **SECTION 4. METHODS**

---

### **4.1. STUDY POPULATION**

This study will investigate lung function in term ( $\geq 37$  weeks) and preterm (22-36 weeks) infants with and without newborn lung diseases (BPD, RDS, TTN, MAS).

#### **4.1.1. Inclusion Criteria**

Infants must meet all of the following criteria to be eligible:

Infants  $\geq 22+0/7$  weeks' gestation at birth.

Infants whose parents/legal guardians have provided consent for enrollment.

Infants admitted to the regional neonatal intensive care unit (RNICU) or the newborn nursery (NBN) at UAB.

Off ventilator/CPAP support for  $\geq 12$  hours before study entry.

#### **4.1.2. Exclusion Criteria**

Infants will be excluded from this study if they have any of the following:

A major congenital malformation (e.g., cardiac disease or diaphragmatic hernia).

A neuromuscular condition that affects respiration (e.g., spinal muscular atrophy or myopathy).

A terminal illness or decision to withhold or limit support (e.g., chromosomal abnormality or neoplasm)

### **4.2. DETAILED STUDY PROCEDURES**

#### **4.2.1. Screening**

The study coordinator will maintain a log of all potentially eligible patients admitted to UAB RNICU and NBN. Infants will be recruited by approaching one or both parents/legal guardians post-natally.

#### **4.2.2. Consent Procedures**

Parents/legal guardians of eligible infants will be approached upon admission to the RNICU or NBN at UAB. Parents will be provided with a copy of the informed consent containing written information about the study and participation in the study as part of the consent process.

#### **4.2.3. Study Intervention and Comparison**

Term and preterm infants with and without newborn lung disease will have serial oscillometry to evaluate neonatal lung function. Infants will have pulmonary function testing performed using the forced oscillation technique at baseline after enrollment in the study. This will be repeated after 24 hours, 48 hours and once per week thereafter among infants who remain hospitalized.

Infants with lung disease who are receiving pulmonary medications or treatments for lung disease, as per physician order, will have additional measurements of pulmonary function before and after these treatments are given.

#### **4.2.4. Control or Monitoring of Co-interventions**

Aim 1 control: baseline oscillometry measurements will be compared over time between preterm infants and term infants without lung disease as defined by need for respiratory support.

Aim 2 control: preterm infants with RDS who go on to develop BPD will be compared with preterm infants with RDS who do not go on to develop BPD. Preterm infants who do not develop BPD will serve as controls for RDS infants who develop BPD.

Aim 3 control: baseline pulmonary function tests and serial changes over time will be compared between infants with and without lung disease. Preterm infants without lung disease will act as controls for preterm infants with lung disease. Term infants without lung disease will act as controls for term infants with lung disease.

Aim 4 control: The timing of pulmonary function testing among infants with lung disease will be recorded in relation to the timing of interventions, as ordered by the treating physician, which may affect pulmonary function including bronchodilators, steroids, diuretics, methylxanthines, different forms of physical therapy, and nebulized/inhaled medications, to determine the effects of these treatments on pulmonary function pairing the pre-treatment pulmonary function values (control) for an individual patient with the post-treatment values (intervention) for the same individual patient.

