### **3.2. SECONDARY HYPOTHESIS OR QUESTIONS (S) (IF APPLICABLE)**

- 1) Oscillometry can detect disease progression (e.g., BPD, RDS, TTN and MAS) and resolution in infants hospitalized in the UAB NICU.
- 2) Oscillometry can inform therapeutic response to common pulmonary interventions (e.g., systemic steroids, inhaled steroids, and diuretics) in infants hospitalized in the UAB NICU.
- 3) To determine how pulmonary function differs over time between preterm infants with RDS which resolves and preterm infants with RDS who go on to develop BPD.
- 4) To determine the effects on pulmonary function measurements of medications and treatments given to newborn infants to treat bronchopulmonary dysplasia including physical therapy, methylxanthines, furosemide, chlorothiazide, inhaled and systemic corticosteroids, cromolyn sodium, and albuterol.

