### 5.1. STATISTICAL ANALYSIS PLAN

Results will be analyzed by the Student's t test, as appropriate for parametric data, and by Mann-Whitney U rank sum test for nonparametric data. A  $p$  value of  $<0.05$  will be considered statistically significant.

Non-independent parametric data will be analyzed by the paired Student's t test, and Wilcoxon signed rank test for non-independent non-parametric data.

Chi-square or Fisher's exact test will be used as appropriate to analyze categorical data.

Analysis of covariance and multiple regression models will be used to examine the interaction between, and the independent effects of factors including birth weight, gestational age, gender, ethnicity, socioeconomic group, maternal smoking, type and severity of lung disease, treatment with surfactant (including number of doses), days of mechanical ventilation before study entry, days of respiratory support before study entry, treatment with antenatal steroids, and treatment with postnatal steroids upon primary and secondary outcomes.

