#### **Aim 4 (Comparison of lung compliance response to therapeutic intervention)**

Methylxanthines - Assuming lung reactance at 7 Hz ( $X_7$ ) measurements will have an absolute 15% difference (more positive) lung compliance following this therapy we plan to recruit 120 infants (60 per arm) assuming power of 90%, type I error rate of 5% and standard deviation of 0.5 of the mean.

Physical therapy - Assuming lung reactance at 7 Hz ( $X_7$ ) measurements will have no significant difference with a non-inferiority margin of 15% following this therapy we plan to recruit 120 (60 per arm) infants assuming power of 90%, type I error rate of 5% and standard deviation of 0.5 of the mean.

Nebulized cromolyn sodium - Assuming lung reactance at 7 Hz ( $X_7$ ) measurements will have no significant difference with a non-inferiority margin of 15% following this therapy we plan to recruit 120 infants (60 per arm) assuming power of 80%, type I error rate of 5% and standard deviation of 0.5 of the mean.

Albuterol - Assuming lung reactance at 7 Hz ( $X_7$ ) measurements will have an absolute 15% difference (more positive) following this therapy we plan to recruit 120 infants assuming power of 90%, type I error rate of 5% and standard deviation of 0.5 of the mean.

Furosemide - Assuming lung reactance at 7 Hz ( $X_7$ ) measurements will have an absolute 20% difference (more positive) following this therapy we plan to recruit 70 infants assuming power of 90%, type I error rate of 5% and standard deviation of 0.5 of the mean.

Chlorothiazide - Assuming lung reactance at 7 Hz ( $X_7$ ) measurements will have an absolute 20% difference (more positive) following this therapy we plan to recruit 70 infants assuming power of 90%, type I error rate of 5% and standard deviation of 0.5 of the mean.

Systemic postnatal steroids for BPD - Assuming lung reactance at 7 Hz ( $X_7$ ) measurements will have an absolute 30% difference (more positive) following this therapy, we plan to recruit 30 infants assuming power of 90%, type I error rate of 5% and standard deviation of 0.5 of the mean.

Inhaled postnatal steroids for BPD - Assuming lung reactance at 7 Hz ( $X_7$ ) measurements will have an absolute 30% difference (more positive) following this therapy we plan to recruit 30

infants assuming power of 90%, type I error rate of 5% and standard deviation of 0.5 of the mean.

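### Aim 4 has no rule for pre/post pairs in which a second Aim 4 therapy was started, stopped or changed, so separating the therapies' effects is largely not pre-specified

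*Combined protocol and SAP*

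**What the plan says.** Section 3.2 asks for the effects on lung function of "physical therapy, methylxanthines, furosemide, chlorothiazide, inhaled and systemic corticosteroids, cromolyn sodium, and albuterol". That makes eight therapies, counting inhaled and systemic corticosteroids separately. All are given as the treating physician orders.

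Section 4.2.3 says that treated infants "will have additional measurements of pulmonary function before and after these treatments are given". It gives no interval between the two tests.

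Section 4.2.4, under Aim 4, says: "The timing of pulmonary function testing among infants with lung disease will be recorded in relation to the timing of interventions". The stated purpose is "to determine the effects of these treatments on pulmonary function pairing the pre-treatment pulmonary function values (control", with the same infant's post-treatment values as the intervention side.

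On analysis, Section 5.1 says: "Non-independent parametric data will be analyzed by the paired Student's t test", with the Wilcoxon signed rank test as the nonparametric alternative. It also lists factors for analysis of covariance and multiple regression, ending with "treatment with antenatal steroids, and treatment with postnatal steroids upon primary and secondary outcomes". Postnatal steroids are the only Aim 4 therapy named there.

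Section 5.2 sizes each therapy separately. Albuterol has an "absolute 15% difference (more positive) following this therapy we plan to recruit 120 infants assuming power of 90" percent. Furosemide and chlorothiazide each have an "absolute 20% difference (more positive) following this therapy we plan to recruit 70 infants". Systemic and inhaled steroids each have 30% with 30 infants. Physical therapy and cromolyn each have a 15% non-inferiority margin with 120 infants.

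**The concern.** The eight therapies are listed as treatments for the same disease, so one infant may receive several. If two are started or changed between a pre and a post test, the pair shows their joint effect. A paired test has no term for the second therapy, and there is no concurrent untreated group. The plan neither excludes such a pair, nor requires stable background treatment, nor assigns the change.

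A therapy with no effect could then take on the effect of whatever was ordered with it, and one change could serve as evidence for two therapies. For physical therapy and cromolyn the error runs the other way: a co-therapy that improves X7 could hide a worsening and falsely support non-inferiority. The question at stake is the one in Section 3.2 about individual treatments.

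**Working it through.** **Inputs.** From Section 5.2 (Aim 4): effects of 0.15, 0.20 and 0.30 of the mean; sizes of 120, 70 and 30; power 90%; type I error 5%; SD 0.5 of the mean. Assumed: the test is two-sided; 0.5 is the SD of the within-infant change; the share *f* of pairs that also span a second therapy is 10%, 25% or 50%.

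**Step 1: the plan's own sizes.** For a paired test, n = (SD × (z₀.₉₇₅ + z₀.₉₀) / δ)², with 0.5 × (1.960 + 1.282) = 1.621.

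| Effect δ | Normal approximation | Exact t | Stated | Two-sample need, per arm |
|---|---|---|---|---|
| 0.15 | (1.621/0.15)² → 117 | 119 | 120 | 234 |
| 0.20 | (1.621/0.20)² → 66 | 68 | 70 | 132 |
| 0.30 | (1.621/0.30)² → 30 | 32 | 30 | 59 |

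The stated sizes fit a paired test and not a two-group one. Some paragraphs speak of 60 per arm, but two groups of 60 would have only about 38% power for a 15% difference. The inference therefore rests on the uncontrolled pre/post change.

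**Step 2: a therapy with zero effect.** Let a share *f* of its pairs also span a therapy with effect *e* from Section 5.2.

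- Mean credited change = f × e
- Variance of change = 0.25 + f(1 − f)e²
- Chance of p < 0.05 from the noncentral t with noncentrality mean/SD × √N

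Example, N = 120, e = 0.20, f = 0.5: mean 0.10; variance 0.25 + 0.25 × 0.04 = 0.26; SD 0.510; noncentrality 0.10/0.510 × √120 = 2.15; chance 57%.

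| Null therapy's N, co-therapy effect | f = 10% | f = 25% | f = 50% |
|---|---|---|---|
| 120, +20% | 7% | 19% | 57% |
| 120, +30% | 10% | 35% | 88% |
| 70, +20% | 6% | 13% | 37% |
| 70, +30% | 8% | 22% | 66% |
| 30, +30% | 6% | 12% | 33% |

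With f = 0 the rate is 5% in every row. A weaker co-therapy gives less: by the same formula, +15% with N = 30 gives 5%, 7% and 12%.

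**Step 3: non-inferiority.** Improvement is a more positive X7, so on the ordinary reading the 15% margin limits worsening. A true 15% worsening combined with a +20% co-therapy in half the pairs shows as −15 + 0.5 × 20 = −5%, well inside the margin.

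**Step 4: cost of dropping overlapping pairs.** Power of the paired t test on N(1 − f) pairs:

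| Stated N (effect) | f = 0 | f = 10% | f = 25% | f = 50% |
|---|---|---|---|---|
| 120 (15%) | 90% | 87% | 80% | 63% |
| 70 (20%) | 91% | 88% | 81% | 63% |
| 30 (30%) | 89% | 85% | 77% | 58% |

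To keep the stated number of single-therapy pairs, recruitment of N/(1 − f) would be 134, 78 and 34 at 10%; 160, 94 and 40 at 25%; and 240, 140 and 60 at 50%.

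**The case against.** Four stronger readings are tempting, and the documents do not support them.

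- A reader might infer that the planned models cannot separate the therapies. Section 5.1 presents its factor list as open-ended and Section 4.2.4 records treatment timing, so terms could be added. What stands is that, apart from postnatal steroids, none is pre-specified, and the steroid factor is not tied to the interval between tests.
- A reader might infer that the plan directs an overlapping pair to be counted for both therapies. It is silent. Nothing stops the double count, and a paired test run therapy by therapy would produce it.
- A reader might take the +30% rows as typical. Only steroids carry that assumed effect, and they are the one Aim 4 therapy listed for adjustment. The rows with a +20% co-therapy (6–7%, 13–19% and 37–57%) do not depend on steroids.
- A reader might set a spurious +15% against the 15% margin and conclude that physical therapy or cromolyn would fail. The direction is wrong: improvement moves the estimate away from the limit.

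It is also fair to say that overlap may be rare. Tests close to a single dose would seldom span a second therapy, while tests around a multi-day course might often do so. With no interval stated, neither can be assumed. The therapy questions are secondary, in an observational study. Overlap could be identified later from recorded timing, but a rule chosen after the data are seen is not pre-specified.

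**Conclusion.** The point holds as a gap in the Aim 4 analysis. Each therapy's effect is read from an uncontrolled paired change, no rule covers pairs that a second Aim 4 therapy could have influenced, and six of the eight therapies have no pre-specified adjustment. In the five pairings tabulated, a null therapy reaches p < 0.05 in about 6–10% of studies at 10% overlap, 12–35% at 25% and 33–88% at 50%. These figures rest on the assumed overlap share, the effects in Section 5.2, an SD of change of 0.5 and a two-sided 5% test; they show sensitivity and do not forecast the error rate. Aims 1 to 3 and safety are not affected. The change should be made before Aim 4 is analysed.

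**What to change.** Add to Sections 4.2.4 and 5.1:

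1. A pair counts toward a therapy's primary estimate only if, between that pair's two tests, no other Aim 4 therapy was started, stopped or changed in dose, and no new or one-off treatment was given. Other therapy continuing on an unchanged schedule, including scheduled intermittent treatment, is allowed.
2. All other pairs are reported as combination pairs and not attributed to one therapy.
3. As a supporting analysis, all pairs enter one regression of change in X7, with an indicator for each Aim 4 therapy given or changed in the interval.

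Restate the Section 5.2 power for the single-therapy pairs actually obtained.

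Treatment orders and test schedules do not change, and the flag comes from timing that the plan already records. The cost is fewer pairs, with the loss of power or extra recruitment shown in the working, and a possibly selected group, since infants on one changing therapy may differ from the rest. The regression uses the other pairs but can separate only therapies that do not always change together.

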#### **4.2.5. Primary Outcome**

The primary outcome will be change in lung reactance at 7 Hz ( $X_7$ ) quantified by oscillometry in each comparison group.

In Aim 1, we will compare lung function between term and preterm infants without lung disease at baseline, 24 hours, 48 hours, 72 hours, 7 days, and weekly thereafter until discharge.

In Aim 2, we will compare lung function between preterm infants with RDS who develop BPD and those who do not develop BPD.

In Aim 3, we will longitudinally evaluate change in lung function in NICU patients with lung disease (BPD, RDS, TTN, MAS) at diagnosis, 24 hours, 48 hours, 72 hours, 7 days, and weekly thereafter until resolution of disease state or NICU discharge.

In Aim 4, we will longitudinally evaluate lung function response to therapeutic intervention.

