### **Study Design Type**

This will be a prospective observational study with pre-specified Aims and Hypotheses. Oscillometry will be performed in term and preterm infants with and without lung disease. Our study will analyze lung function measures obtained in conjunction with routine clinical care in the NICU, as well as normative comparison data obtained from healthy full-term infants in the well-baby nursery. Both cross-sectional (term vs preterm; BPD vs non-BPD) and longitudinal comparisons (disease progression and therapeutic response) will be performed.

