#### **4.2.6. Secondary Outcomes**

Secondary measures of lung function will be comparison of resistance data at available frequencies including r7, r13, and r19; reactance at other available frequencies including 13 and 19 Hz, impedance data including resistance as a function of frequency  $R(f)$ , reactance as a function of frequency  $X(f)$ , and coherence at each frequency  $Coh(f)$ ; resonance frequency ( $f_{res}$ ); reactance area  $AX7$ ; reactance difference  $\Delta X7$ ; tidal volume and respiratory rate. In addition measures over time will allow us to create normative data curves of changes in these measurements over time in the given populations.

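### Term control values from about 7 days on come only from infants still in hospital, so they may not represent healthy term infants in the Aim 1 comparison, the TTN/MAS controls or the normative curves

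*Combined protocol and SAP*

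**What the plan says.** Four parts of the combined protocol and SAP bear on this.

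- **Who the term reference is.** The abstract (Study Design Type) describes "normative comparison data obtained from healthy full-term infants in the well-baby nursery". The eligible pool is wider, however: section 4.1.1 admits "Infants admitted to the regional neonatal intensive care unit (RNICU) or the newborn nursery (NBN) at UAB". Section 4.2.4 defines absence of lung disease, for the Aim 1 controls, only by the need for respiratory support.
- **When infants are tested.** Section 4.2.3: "This will be repeated after 24 hours, 48 hours and once per week thereafter among infants who remain hospitalized". No test after discharge is described.
- **What is compared.** For Aim 1, section 4.2.5 plans to "compare lung function between term and preterm infants without lung disease at baseline, 24 hours, 48 hours, 72 hours, 7 days", continuing weekly until discharge.
- **What else the later term values are used for.** In section 4.2.4, for Aim 3, baseline and serial changes are compared with controls: "Term infants without lung disease will act as controls for term infants with lung disease". Section 4.2.6 expects measures over time to "create normative data curves of changes in these measurements over time in the given populations".

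Section 5.2 sizes Aim 1, and the TTN and MAS comparisons in Aim 3, on initial measurements only. Section 5.1 lists t, rank, paired and categorical tests, analysis of covariance and multiple regression. It gives no method for values missing because an infant was discharged, and reason for stay is not among its covariates.

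**The concern.** Measurement ends at discharge, and discharge is related to health. A term infant without lung disease who still contributes a value at 7 days or later is in hospital for some reason that most of the nursery cohort presumably does not share. The control definition does not screen for such reasons, because an infant who needs no respiratory support still qualifies.

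Three readings of the data are at stake. The later term-versus-preterm difference could mix maturation with selection. The later part of a term normative curve could be taken as normal newborn values when it describes hospitalized infants. The later course of TTN or MAS could be judged against controls who are not healthy. Enrolling more infants would not cure this, because the problem is who remains and not only how many.

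**Working it through.** **1. The plan's own figure.** Inputs from section 5.2, Aim 1: difference 0.20 of the mean, SD 0.50 of the mean, type I error 5%, power 90%. Sidedness is not stated.

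n per group = 2 × (1.960 + 1.282)² × 0.50² / 0.20² = 131.3, rounded up to 132, total 264.

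This reproduces the stated 264 with a two-sided test (one-sided would give 108 per group). The figure is sound for the initial measurement, which is the only time point it covers.

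**2. Who can contribute a later term value.** Setting the sections side by side:

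| Step | Source |
|---|---|
| Intended term reference is the healthy nursery infant | Abstract, Study Design Type |
| NICU infants are also eligible | 4.1.1 |
| Control status depends only on respiratory support | 4.2.4, Aim 1 |
| Tests are repeated only while in hospital | 4.2.3 |
| Comparison continues at 7 days and weekly | 4.2.5 |

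A later term control value therefore requires that the infant is still in hospital and needs no respiratory support. Section 4.1.2 excludes major malformation, neuromuscular conditions affecting respiration, and terminal illness or limitation of support. That narrows the group but leaves other reasons for a long stay.

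**3. Illustration of the loss in numbers.** The documents give no length of stay, so the share remaining is an assumption, shown as a range. Two-sample t test, two-sided 5%, standardized difference d = 0.20/0.50 = 0.4, noncentrality = 0.4 / √(1/n_term + 1/n_preterm). All 132 preterm infants are kept.

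| Share of 132 term remaining (assumed) | Term n | Noncentrality | Power |
|---|---|---|---|
| 100% | 132 | 3.25 | 90% |
| 50% | 66 | 2.65 | 75% |
| 25% | 33 | 2.06 | 53% |
| 10% | 13 | 1.38 | 28% |
| 5% | 7 | 1.03 | 18% |

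Keeping all the preterm infants is generous. If only 66 of them also remain, 7 term infants give about 17%.

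**4. Illustration of selection.** Suppose (assumption, not from the documents) that the remaining term infants' X7 is 0.10 of the mean more negative than that of all healthy term infants. A true term-preterm difference of 0.20 would then appear as 0.20 − 0.10 = 0.10. A shift the other way would enlarge it. The documents give no basis for either the size or the direction.

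**The case against.** The strongest reply is that the premise is not documented. No section gives length of stay or reasons for stay. A reader might infer that healthy term infants have all left by 48 or 72 hours, or that every term infant present at 7 days is ill. The documents support neither. Some healthy infants may still be in the nursery at 72 hours, so the point is weaker there. Visits are also counted from enrollment rather than birth, so a fixed 48-hour cut-off has no basis in the text. This objection stands, and it limits the point to values from about 7 days on, with 72 hours as a lesser possibility. (Section 4.2.5 lists a 72-hour comparison that the 4.2.3 schedule lacks. That mismatch needs reconciling separately, and adding the test would not remove the selection.)

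A second reply is that bias in X7 is not shown. A stay for a reason unrelated to the lungs need not alter reactance, and the exclusions already remove several conditions. This also stands: the later values *may* be biased, and it cannot be said that they are.

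Third, a reader might infer that the study is underpowered for Aim 1. It is not on this ground. Section 5.2 claims power for initial measurements only, and those comparisons, including TTN and MAS, are untouched.

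Fourth, the plan is open about testing only until discharge, and section 4.2.7 has clinical history recorded. That makes reasons for stay potentially reportable, but it does not stop the later values being used as healthy comparators or as normative. Nor can the regression models in 5.1 recover healthy infants who have left.

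Finally, selective discharge is not confined to term infants. Preterm infants without lung disease, who are the controls for RDS and BPD, are tested under the same rule.

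**Conclusion.** The point holds in a limited form. As written, the plan uses term values from 7 days on as comparator, serial control and normative data, although those values come from infants selected by remaining in hospital, and neither the control definition nor section 5.1 deals with that. The selection follows from the text. Its extent, and the size and direction of any effect on X7, do not, because length of stay and reason for stay are not given. The power figures (about 53% with 33 term infants and 18% with 7, against 132 preterm) depend wholly on assumed retention and on keeping every preterm infant, and are illustrative only. The baseline comparisons for which the study is sized remain valid in this respect. The later preterm control values may be affected in the same way.

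**What to change.** In sections 4.2.4 to 4.2.6:

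- Make the healthy term-versus-preterm comparison (Aim 1), and the comparison of TTN and MAS infants with term controls (Aim 3), at baseline and the early visits, while the nursery cohort is still largely in hospital.
- Treat term control values from 7 days on as descriptive. Label them *term infants still hospitalized*, and report at each visit the number remaining and the reasons for stay.
- Leave infants whose stay is prolonged for illness out of the healthy-term normative curve.
- Read later TTN and MAS values as change within the infant.
- Report the numbers remaining in the same way for preterm controls.

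This is a wording change with no extra oscillometry; reason for stay has to be recorded at each visit if it is not already captured in the clinical history. All collected data are kept. The cost is that the study no longer claims to describe a healthy-term course at the later visits.

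### Sections 4.2.3 and 4.2.5 conflict on whether serial oscillometry in Aim 3 infants continues after the disease resolves; under 4.2.5, values after resolution drop out of Aim 3

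*Combined protocol and SAP*

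**What the plan says.** Section 4.2.3 sets the testing procedure for term and preterm infants with and without lung disease. After the baseline test it states: "This will be repeated after 24 hours, 48 hours and once per week thereafter among infants who remain hospitalized". It has no stop at resolution.

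Section 4.2.5 gives the Aim 3 series as diagnosis, 24 hours, 48 hours, and then "72 hours, 7 days, and weekly thereafter until resolution of disease state or NICU discharge". In the same section the Aim 1 infants, who have no lung disease, are compared "at baseline, 24 hours, 48 hours, 72 hours, 7 days, and weekly thereafter until discharge". The Aim 2 sentence there gives neither a schedule nor a stopping point.

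Section 4.2.4 makes infants without lung disease the controls for Aim 3 and says "baseline pulmonary function tests and serial changes over time will be compared between infants with and without lung disease".

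Section 3.2, item 1, hypothesizes that oscillometry can detect disease progression "and resolution in infants hospitalized in the UAB NICU". Item 3 reads "To determine how pulmonary function differs over time between preterm infants with RDS which resolves" and those whose RDS becomes BPD.

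Section 5.1 lists t tests, rank tests, their paired versions, chi-square or Fisher tests, analysis of covariance and multiple regression. It names no repeated-measures model and no method for follow-up that ends because of disease status.

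**The concern.** The two sections give different end points for the same serial measurement, and they diverge for every infant who recovers before going home. Under 4.2.5, whether an infant has a later value depends on the clinical state that X7 is meant to track.

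Three things are at stake. First, recovered values are what the resolution part of hypothesis 1 needs, and 4.2.5 leaves them out of Aim 3. Second, cases would be followed only while diseased but controls until discharge, so the serial comparison in 4.2.4 would set a shrinking, sicker subset against an unselected group. Third, the primary outcome is a change in X7, and the listed analysis methods do not address this selection. Values not collected after resolution cannot be recovered later.

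**Working it through.** **1. The rules side by side**

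| | 4.2.3 | 4.2.5, Aim 3 | 4.2.5, Aim 1 (controls) |
|---|---|---|---|
| Early tests | baseline, 24 h, 48 h | diagnosis, 24 h, 48 h, 72 h, 7 days | baseline, 24 h, 48 h, 72 h, 7 days |
| Then | weekly | weekly | weekly |
| Ends at | end of hospital stay | resolution or NICU discharge | discharge |

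The schedules also differ on the 72-hour visit, which appears only in 4.2.5. No section defines resolution. Section 4.2.4 uses the need for respiratory support to define absence of lung disease for Aim 1, but does not tie that to resolution.

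**2. One infant (invented dates).** RDS resolves on day 9 and the infant stays to day 40. Under 4.2.3, four weekly tests fall after resolution: days 16, 23, 30 and 37 if weeks are counted from 48 hours, or days 14, 21, 28 and 35 if counted from day 7. Under 4.2.5, none does; at most one test is taken at resolution.

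**3. The plan's own figures (section 5.2, Aim 3).** Inputs: SD 0.5, two-sided 5%, power 90%. Formula: n per arm = 2 × [SD × (1.960 + 1.282) / difference]².

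- Difference 0.20 (RDS, BPD, TTN): 131.34, rounded up to 132 per arm. This matches the plan.
- Difference 0.50 (MAS): 21.01, which rounds up to 22. The plan has 21, where power is still 90.0%.

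All of these comparisons are of initial measurements, so no later stopping rule can change them.

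**4. Illustration of later visits.** Assumptions not in the documents: the deficit in X7 is 0.20 while diseased (borrowed from the planned RDS difference) and 0 once resolved; all 132 infants stay in hospital; a fraction f of those still diseased resolves each week. At week 4:

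- whole-cohort deficit = 0.20 × (1 − f)⁴
- no test at resolution: deficit seen = 0.20, infants measured = 132 × (1 − f)⁴
- last test at resolution: deficit seen = 0.20 × (1 − f), infants measured = 132 × (1 − f)³

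| f | Whole cohort | Seen, no test at resolution (infants) | Seen, test at resolution (infants) |
|---|---|---|---|
| 10% | 0.131 | 0.20 (86.6) | 0.18 (96.2) |
| 30% | 0.048 | 0.20 (31.7) | 0.14 (45.3) |
| 50% | 0.0125 | 0.20 (8.3) | 0.10 (16.5) |

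A final test at resolution reduces the distortion but does not remove it.

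**5. A second illustration.** Suppose X7 is normal with SD 0.5 of the mean, and correlates r with the severity that decides who has resolved. If a fraction f is still diseased and tested, their mean is shifted by r × 0.5 × φ(z_f)/f, where φ is the standard normal density and z_f the cut-off with a fraction f above it. For f = 0.5, φ(0)/0.5 = 0.798, so the shift is 0.100, 0.199 or 0.299 of the mean at r = 0.25, 0.5 or 0.75. At r = 0.5 it is 0.124 for f = 0.7 and 0.290 for f = 0.3. Neither r nor f is given in the documents.

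**The case against.** A reader might infer that resolution is never measured and that later visits hold only sick infants. The text does not support this. Running until resolution can include a test at resolution, and then each later visit also contains infants who have just resolved. What 4.2.5 clearly omits is measurement after resolution.

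A reader might also infer that testing itself stops. Section 4.2.5 is the outcome section and describes what Aim 3 evaluates, whereas 4.2.3 is the procedure. Read together, 4.2.3 may govern collection and 4.2.5 only the Aim 3 window. The values would then exist, and the defect would lie in which of them Aim 3 uses. That reading is fair, but no section states it.

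A third tempting step is to say that the comparison of resolving RDS with RDS that becomes BPD loses late data in one group. That comparison is Aim 2, whose sentence in 4.2.5 carries no resolution stop, so the 4.2.3 schedule applies unless the Aim 3 stop is carried over to the same infants.

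Finally, the late-visit shift should not be set against the planned 20% difference. That difference concerns initial X7. The shift describes visit means, whereas section 5.1 also provides paired tests. Pairing does not remove all selection, but the figures above do not measure the bias in a paired analysis.

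After all this, the conflicting end points, the undefined resolution and the unequal follow-up of cases and controls still stand.

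**Conclusion.** The concern holds in a limited form. Sections 4.2.3 and 4.2.5 disagree on when serial measurement ends for infants with lung disease, and the plan does not say which governs. If 4.2.5 governs, Aim 3 has no values after resolution and at most one per infant at resolution. Its later visits lean toward unresolved disease while controls continue to discharge, and hypothesis 1 on resolution is weakly supported. The sample sizes and the initial X7 comparisons are sound on this point, and Aim 2 is affected only conditionally.

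The direction of the late-visit distortion is clear if X7 tracks severity. Its size is not known: the figures rest on assumed resolution rates and correlations and on a planning SD for initial measurements, so they are illustrative only. The point should be settled before enrollment proceeds far, but it does not invalidate the design.

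**What to change.** - Reconcile 4.2.3 and 4.2.5 so that Aim 3 research measurements and analysis follow the existing 4.2.3 schedule while the infant is hospitalized. Align the 72-hour visit, which only 4.2.5 lists.
- Define resolution for each disease, and record its date as a variable rather than as the end of follow-up. The clinical content of the definition is for the investigators.
- Keep resolved infants who are still in hospital in the serial Aim 3 analysis under their original diagnosis. Let infants who progress from RDS to BPD also enter the BPD comparison from the time of BPD diagnosis.
- For hypothesis 1, compare each infant's last test before resolution with the first test after it. The paired methods in 5.1 already allow this.
- State in 5.1 how the serial analysis treats follow-up of unequal length. Give as a limitation that discharge still removes recovered infants, so selection is reduced rather than eliminated.

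The cost is a few sentences in 4.2.5 and 5.1, and a few more brief mask tests per infant than under the narrower rule. Section 4.2.3 already schedules those weekly tests. The change concerns research measurement, not treatment.
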